### Stratification by ERß alleles and test of interaction:

Analysis of hypothesis above (C0- C07 and corresponding models) will be stratified by genotype of

Analysis plan: PRODICA, [name]
---------------------------------------

ERβ (variable: cat\_genotype).

Interactions between exposure and ERß SNPs on the outcome will be evaluated on the additive effect scales. Effects will be measured by RDs and interaction will be assessed in a generalized linear model by the product term between the covariates representing phytoestrogen intake and SNP genotypes.

Product term: int1=intervention\*cat\_genotype

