### HYPOTHESIS

- In men diagnosed with intermediate risk-level prostate cancer, the addition of phytoestrogenrich foods containing 200 mg phytoestrogens per day in six weeks, gives a reduced prostate tumor proliferation compared to an absence of the addition of phytoestrogen-rich foods during the same period.
- 2) If the effect of phytoestrogens on prostate tumor proliferation exists, it is modified by a SNP in the promoter region of the estrogen-beta-gene (rs 2987983-13950).

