### Covariates to test (possible confounding factors):

- Energy\_kcal\_EP\_3 (total energy intake at endpoint, categorized in tertiles)
- Sum\_satured\_fat\_EP\_3 (sum of saturated fats (g) at endpoint, categorized in tertiles)
- Fat\_fish\_group\_EP (categorized intake of fat fish at endpoint)
- Calcium\_EP\_3 (intake of calcium at endpoint, categorized in tertiles)
- Physical\_activity\_BL\_group (categorized physical activity at baseline)
- f47\_1\_EP (changed physical activity during intervention)
- Biopsies\_cancer (percent of biopsies with cancer at diagnosis)
- gleason\_cat (categorized Gleason score at diagnosis)
- gleason\_cat\_rp (categorized Gleason score at surgery)
- rp\_teritargradjanej (categorized tertiary Gleason degree at surgery)
- Age\_inclusion (continuous age at baseline)
- BMI\_group (BMI at baseline in groups)
- Weight\_diff (difference in weight between endpoint and baseline)
- smoking (categorized smoking at baseline)
- heredity (categorized heredity at baseline)
- Zinc\_EP\_3 (intake of zinc at endpoint, categorized in tertiles)
- Alcohol\_EP\_3 (intake of alcohol at endpoint, categorized in tertiles)
- Sum\_monosat\_fat\_EP\_3 (intake of monounsaturated fatty acids at endpoint, categorized in tertiles)
- Sum\_polysat\_fat\_EP\_3 (intake of polyunsaturated fatty acids at endpoint, categorized in tertiles)
- red\_meat\_EP\_3 (intake of red meat at endpoint, categorized in tertiles)
- vegetables\_all\_EP\_3 (intake of vegetables at endpoint, categorized in tertiles)
- fruit\_all\_EP\_3 (intake of fruits at endpoint, categorized in tertiles)
- Vit\_E\_EP\_3 (intake of vitamin E at endpoint, categorized in tertiles)

• Finasteride (intake of Finasteride under intervention, no=0, yes=1)

Pearson or Spearman correlation coefficient will be used to evaluate whether dietary covariates are correlated. If the correlation coefficient between two covariates in the model or between covariates and the main exposure are higher than 0.6, multicolinearity issues is considered, eventually one of the covariates will be excluded from the model.

Model building:

The association between intake of phytoestrogens and tumor proliferation will evaluated by regression models, providing estimate of risk difference (RD) relative risk (RR) and corresponding 95% confidence intervals.

Crude models:

C0: Ki-67

C1: C0 + Group\_intervention C2: C0 + Phytoestogens\_EP C3: C0 + Isoflavones\_EP C4: C0 + Lignans\_EP C5: C0 + Coumestrol\_N58\_EP

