C02: PSA\_total\_diff C12: C02 + Group\_intervention C22: C02 + Phytoestogens\_EP C32: C02 + Isoflavones\_EP C42: C02 + Lignans\_EP C52: C02 + Coumestrol N58 EP

C03: PSA\_ratio\_diff C13: C03 + Group\_intervention C33: C03 + Phytoestogens\_EP C43: C03 + Isoflavones\_EP C53: C03 + Lignans\_EP C63: C03 + Coumestrol N58 EP

C04: estradiol\_diff\_cat C14: C04 + Group\_intervention C34: C04 + Phytoestogens EP C44: C04 + Isoflavones\_EP C54: C04 + Lignans\_EP C64: C04 + Coumestrol N58 EP

C05: testo\_diff\_cat C15: C05 + Group\_intervention C35: C05 + Phytoestogens\_EP C45: C05 + Isoflavones\_EP C55: C05 + Lignans\_EP C65: C05 + Coumestrol\_N58\_EP

 $\underline{C0_6:} testo_estrad_ratio_diff$   $C1_6: C0_6 + Group\_intervention$   $C3_6: C0_6 + Phytoestogens\_EP$   $C4_6: C0_6 + Isoflavones\_EP$   $C5_6: C0_6 + Lignans\_EP$   $C6_6: C0_6 + Coumestrol\_N58\_EP$ 

C07: testo\_SHBG\_ratio\_diff C17: C07 + Group\_intervention C37: C07 + Phytoestogens\_EP C47: C07 + Isoflavones\_EP C57: C07 + Lignans\_EP C67: C07 + Coumestrol\_N58\_EP

Final model:

Which covariates included in the model will be based on:

- 1) If a known risk factor for the outcome (based on previous subject matter knowledge and with the help of Directed Acyclic Graphs)
- 2) If differs between groups of exposure
- 3) proportional ( $\geq 10\%$ ) change in  $\beta$ -coefficients

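### No single test is named to decide hypothesis 2: the genotype interaction is not tied to Ki-67 and the genotype analysis spans 35 models

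*SAP*

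**What the plan says.** Under Hypothesis, the second claim is: "If the effect of phytoestrogens on prostate tumor proliferation exists, it is modified by a SNP in the promoter region of the estrogen-beta-gene". It names one effect (on proliferation) and one SNP, and it is conditional on the effect existing.

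The section on stratification by ERβ alleles and test of interaction sets the scope differently: "Analysis of hypothesis above (C0- C07 and corresponding models) will be stratified by genotype of" ERβ. The crude models it points to begin with Ki-67 and five exposures: "C1: C0 + Group\_intervention C2: C0 + Phytoestogens\_EP C3: C0 + Isoflavones\_EP C4: C0 + Lignans\_EP C5: C0 + Coumestrol\_N58\_EP". The same five exposures are then repeated for total PSA change, PSA ratio change, categorised estradiol change, categorised testosterone change, testosterone/estradiol ratio change and, last, testosterone/SHBG ratio change ("testo\_SHBG\_ratio\_diff C17: C07 + Group\_intervention").

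Interaction is to be assessed "by the product term between the covariates representing phytoestrogen intake and SNP genotypes", which could mean any of the exposures. The only term then written out is "Product term: int1=intervention\*cat\_genotype", with no outcome attached.

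Two definitions elsewhere bear on this. The primary outcome section gives three Ki-67 summaries (median, mean, maximum), each also dichotomised, and the model labelled C0 does not choose among them. The effect-modifier section codes level 0 of `cat_genotype` as TT and level 1 as TT/CC, so TT appears in both levels and TC in neither.

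**The concern.** The hypothesis and its analysis differ in scope. The hypothesis concerns proliferation; the genotype analysis also takes in two PSA outcomes and four hormone outcomes. It also adds four self-reported intake exposures to the randomised comparison. The SAP does not say which of the resulting interactions answers hypothesis 2. Nor does it give a significance level or multiplicity rule for these tests, or label any of them exploratory.

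The gap remains within Ki-67. Five exposures and up to six Ki-67 versions give 5 × 6 = 30 possible interaction tests, all compatible with the text. At stake is what the trial may conclude about effect modification. With no deciding test fixed in advance, a positive or a negative answer to hypothesis 2 can depend on which model is reported.

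**Working it through.** The SAP states no error rate or power for the genotype analysis, so there is no figure of its own to reproduce.

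**Inputs**
- Outcomes: 7 (Ki-67 counted once, two PSA, four hormone or hormone-ratio), from the crude model list.
- Exposures per outcome: 5 (randomised group, total phytoestrogens, isoflavones, lignans, coumestrol), same list.
- Product terms per outcome: 1 if only `int1` is meant, 5 if the general sentence is meant.
- Alpha: not stated. Assumed 0.05 two-sided per test, to match the plan's intention of "providing estimate of risk difference (RD) relative risk (RR) and corresponding 95% confidence intervals".
- Correlations among test statistics: not available. Assumed 0 to 0.5 between outcomes and 0 to 0.9 between exposures.

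**Counts**
- All models: 7 × 5 = 35.
- `int1` only: 7 × 1 = 7.

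**Chance of at least one false-positive interaction with no true effect modification**

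For k independent tests this is 1 − 0.95^k:
- k = 7: 1 − 0.95^7 = 0.302; expected false positives 7 × 0.05 = 0.35.
- k = 35: 1 − 0.95^35 = 0.834; expected false positives 35 × 0.05 = 1.75.

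For correlated tests, null z-statistics were simulated on a 7 × 5 grid (7 × 1 for `int1` only), with a common correlation between outcomes and another between exposures, 100,000 runs per setting:

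| Tests | Outcome correlation | Exposure correlation | P(at least one p < 0.05) |
|---|---|---|---|
| 7 | 0 | – | 0.301 |
| 7 | 0.3 | – | 0.269 |
| 7 | 0.5 | – | 0.231 |
| 35 | 0 | 0 | 0.833 |
| 35 | 0.3 | 0.6 | 0.675 |
| 35 | 0.5 | 0.8 | 0.493 |
| 35 | 0.5 | 0.9 | 0.413 |

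The ranges are therefore about 23–30% for 7 tests and 41–83% for 35. No sample size or genotype frequency enters these calculations.

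**Sensitivity to the Ki-67 definition.** Counting the three Ki-67 summaries separately gives 9 outcomes and 9 × 5 = 45 models. The independence value is then 1 − 0.95^45 = 0.901. This is an upper guide only, since the three summaries come from the same specimens and will be correlated.

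**With one designated test** the chance is 0.05. If all 35 were kept confirmatory, a Bonferroni threshold would be 0.05/35 = 0.0014 per test.

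**The case against.** The strongest reply is that the SAP already ranks its outcomes. Ki-67 is defined as primary, PSA comes under the secondary outcomes with hormones following, and model building is framed around tumour proliferation. The expression about analysing the hypothesis recurs under Additional analysis for the antibiotic and finasteride strata, so it may be shorthand for the set of models. This stands. A reader might infer that a PSA or hormone interaction counts as much towards hypothesis 2 as a Ki-67 one; the outcome labels do not support that.

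Second, only one product term is written out, so the strict reading is 7 tests, not 35. A narrower reading is possible: effects are to be measured as risk differences, and among the outcomes as listed only the two categorised hormone changes are binary, plus Ki-67 if dichotomised. Three tests give 1 − 0.95^3 = 14%. This also stands as far as it goes, but the general sentence about intake covariates leaves the wider reading open, and 14% is still nearly three times nominal.

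Third, a reader might count significance in one genotype but not the other as support. On that rule the chance of at least one discordant result among 35 models, with no effect in either stratum, would be 65–97%. The SAP states no such rule: it gives the interaction question to the product term.

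Finally, the protocol is not shown and may rank the tests. That cannot be excluded, but the SAP's own section would still not identify the deciding test.

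**Conclusion.** The point holds as a failure to name the deciding test. Hypothesis 2 is about proliferation, the genotype analysis covers 35 models, and `int1` is not tied to Ki-67 or to one version of it. The false-positive chance for some interaction is about 23–30% on the strict reading and about 41–83% on the wide one, against 5% for a single test. These figures rest on an assumed two-sided alpha of 0.05 per test, no true effect modification and assumed correlations.

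It would go too far to say that a chance genotype difference is likely and will be read as support. On the strict reading the chance is below one in three, and how such a result would be interpreted is an inference rather than something the SAP states. The change is worth making because it settles what the trial can conclude and needs only wording.

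**What to change.** In the section on stratification by ERβ alleles:

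1. State that hypothesis 2 is decided by the `Group_intervention` by `cat_genotype` product term for one Ki-67 variable in all randomised men. Choose that variable from the versions in the primary outcome section before the data are analysed; without this step the Ki-67 model is still not one test.
2. Correct the coding of `cat_genotype` in the effect-modifier section so that it separates TT from the other genotypes.
3. Report genotype-specific Ki-67 effects descriptively, beside the interaction estimate and its 95% confidence interval.
4. Label the genotype analyses of PSA, hormones and the intake exposures exploratory.

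Formal gating of this test on hypothesis 1 would match the conditional wording of hypothesis 2 but is optional: an effect confined to one genotype could be diluted overall, and a gate would then block its detection. The sponsor should say which is intended.

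The cost is SAP wording only; no analysis is dropped and no new data are needed. The downside is that a genotype difference seen only in a PSA, hormone, intake or other Ki-67-version model could not be claimed as confirming hypothesis 2.

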# **Definition of exposure**

The participants in the intervention group are defined as exposed and the participants in the control group are defined as not exposed.

**Group\_intervention** (0=control, 1=intervention)

Intake of different phytoestrogens at endpoint is based on information from the Food Frequency Questionnaire (FFQ) and the 24-h dietary recall.

**Phytoestogens\_EP\_3** (intake of phytoestrogens at endpoint divided in tertiles, calculated from the FFQ)

Lignans\_EP\_3 (intake of lignans at endpoint divided in tertiles, calculated from the FFQ)

Isoflavones\_EP\_3 (intake of isoflavones at endpoint divided in tertiles, calculated from the FFQ)

Coumestrol\_N58\_EP\_2 (dichotomized intake of coumesterol at endpoint, calculated from the FFQ)

Phyto\_24\_recall\_3 (intake of phytoestrogens at the 24-h dietary recall divided in tertiles)

The concentrations of phytoestrogens (daidzein, enterodiol, enterolactone, equol, genistein, glycetein,

Analysis plan: PRODICA, [name]
----------------------------	--------------

lariciresinol, and secoisolariciresinol) in plasma for a sub-group of participants:

**lignans\_EP\_nmol** (plasma levels of lignans at endpoint=enterolactone+ enterodiol+ lariciresinol+ seco\_EP\_nmol)

**lignans\_BL\_nmol** ((plasma levels of lignans at baseline=enterolactone+ enterodiol+ lariciresinol+ seco\_EP\_nmol)

**isoflavones\_EP\_nmol** (plasma levels of isoflavones at endpoint = daidzein\_EP\_nmol + genistein EP nmol + glycitein EP nmol + equol EP nmol)

**isoflavones\_BL\_nmol** (plasma levels of isoflavones at baseline = daidzein\_EP\_nmol + genistein\_EP\_nmol + glycitein\_EP\_nmol + equol\_EP\_nmol)

**phytoestrogens\_EP\_nmol** (plasma levels of total phytoestrogens at baseline = enterolactone\_EP\_nmol + enterodiol\_EP\_nmol + lariciresinol\_EP\_nmol + seco\_EP\_nmol + daidzein\_EP\_nmol + genistein\_EP\_nmol + glycitein\_EP\_nmol + equol\_EP\_nmol)

phytoestrogens\_BL\_nmol (plasma levels of total phytoestrogens at endpoint =
enterolactone\_BL\_nmol + enterodiol\_BL\_nmol + lariciresinol\_BL\_nmol + seco\_BL\_nmol +
daidzein\_BL\_nmol + genistein\_BL\_nmol + glycitein\_BL\_nmol + equol\_BL\_nmol)

lignans\_diff\_nmol = lignans\_EP\_nmol - lignans\_BL\_nmol

isoflav\_diff\_nmol= isoflavones\_EP\_nmol - isoflavones\_BL\_nmol

phyto\_diff\_nmol= phytoestrogens\_EP\_nmol - phytoestrogens\_BL\_nmol

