### Additional analysis:

Intention-to-treat-analyses: All participants will be included.

*Per-protocol-analyzes*: All participants with  $\geq 80$  % compliance will be included.

In the intervention group, compliance will be considered as  $\geq 80$  percent of the recommended intake of 200 mg of phytoestrogens, which is equal to  $\geq 160$  mg. In the control group, intakes below 160 mg of phytoestrogens will be considered compliant.

Analysis of hypothesis will be stratified for:

- no use of antibiotics vs. use of antibiotics
- no use of finasteride vs. use of finasteride

Investigate the effects of the intervention diet on plasma concentrations of phytoestrogens: Cohen's Kappa will be used to compare the agreement of classifications in tertiles from estimated intake of phytoestrogens and plasma concentrations of phytoestrogens. (Kappa values <0 will be considered as poor, 0.00-0.20 as slight, 0.21-0.40 as fair, 0.41-0.60 as moderate, 0.61-0.80 as substantial, and 0.81-1.00 as almost perfect). Boxplots will be used to present the data graphically. Linear regressions will be used to investigate the relationships between estimated intake concentrations (explanatory variables) and plasma concentrations of phytoestrogens (outcomes). The regression model will be stratified according to the intervention- and control groups and genotype.

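### The SAP describes intake-by-genotype product terms but writes out only arm by genotype, leaving 28 genotype-stratified intake models without a specified interaction term

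*SAP*

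**What the plan says.** The second hypothesis in the SAP concerns effect modification: "If the effect of phytoestrogens on prostate tumor proliferation exists, it is modified by a SNP in the promoter region" of the estrogen receptor beta gene.

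Under *Definition of exposure*, exposure is first the randomised arm: "The participants in the intervention group are defined as exposed and the participants in the control group are defined as not exposed". The same section then adds reported intake: "Intake of different phytoestrogens at endpoint is based on information from the Food Frequency Questionnaire (FFQ) and the 24-h dietary recall".

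The crude models for Ki-67 enter the arm and four intake variables one at a time: "C1: C0 + Group\_intervention C2: C0 + Phytoestogens\_EP C3: C0 + Isoflavones\_EP C4: C0 + Lignans\_EP C5: C0 + Coumestrol\_N58\_EP". The same five exposures are repeated for six further outcomes.

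The section on stratification by ERβ alleles makes three statements:

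- Every model is stratified: "Analysis of hypothesis above (C0- C07 and corresponding models) will be stratified by genotype of" ERβ.
- Interaction is assessed on the additive scale in a generalized linear model, "by the product term between the covariates representing phytoestrogen intake and SNP genotypes".
- One term is written out: "Product term: int1=intervention" multiplied by `cat_genotype`.

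Under *Additional analysis*, the SAP also plans strata by antibiotic use and by finasteride use ("Analysis of hypothesis will be stratified for" these two factors). It mentions no product term for them.

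**The concern.** The sentence on interaction speaks of covariates, in the plural, that represent intake. The formula after it contains only the randomised arm. An analyst could therefore fit one arm-by-genotype term per outcome, or one term for each of the five exposures. The SAP does not settle which.

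The choice matters because the intake models are still split by genotype. If a stratified pair of estimates is reported without a matching product term, the natural comparison is whether one stratum is significant and the other is not. That comparison is not a test of interaction, and it often shows a contrast when the effect is the same in both strata. Genotype modification is one of only two hypotheses in the SAP, so the terms that bear on it should be fixed before the data are seen.

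**Working it through.** The SAP gives no power, alpha or genotype split for this analysis, so there is no figure of its own to reproduce. The check is a count, a matching of terms to models, and an illustration under stated assumptions.

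**1. Count of models.** The outcomes are Ki-67, change in total PSA, change in PSA ratio, estradiol change category, testosterone change category, change in testosterone/estradiol ratio and change in testosterone/SHBG ratio, 7 in all. The exposures are the arm, total phytoestrogens, isoflavones, lignans and coumestrol, 5 in all.

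- Crude models: 7 × 5 = 35.
- Arm models: 7 × 1 = 7.
- Intake models: 7 × 4 = 28.
- Fits after stratifying by two genotype groups: 35 × 2 = 70.

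**2. Matching terms to models.** `int1` fits the 7 arm models. No term is written for `Phytoestogens_EP`, `Isoflavones_EP`, `Lignans_EP` or `Coumestrol_N58_EP`, here or elsewhere in the SAP. `int1` cannot stand in for them, because a product with the arm does not test whether genotype modifies the effect of an intake variable.

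**3. Form of the intake variables.** *Definition of exposure* gives tertiles (suffix `_3`) for total phytoestrogens, isoflavones and lignans, and a dichotomy (suffix `_2`) for coumestrol. The model lists use the names without a suffix, which *Variables to analyze* builds as sums in µg for the first three. A product with a two-level genotype has 1 degree of freedom if intake is continuous or dichotomised and 2 if it is in tertiles. The form must be fixed before the term can be.

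**4. Genotype coding.** *Definition of effect modifying factor* codes `cat_genotype` as 0 for TT and 1 for TT/CC. TT is in both levels and TC is in neither. Every product with this variable, `int1` included, is ill-defined until this is corrected.

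**5. Illustration of what a stratum comparison does.** Assumptions, none from the SAP: two-sided 0.05, no true interaction, overall power P, and a share f of men in one stratum.

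- Overall standardised effect: d = 1.96 + z(P).
- Power in a stratum with share s: Φ(d√s − 1.96) + Φ(−d√s − 1.96), with s = f in one stratum (giving p1) and s = 1 − f in the other (giving p2).
- Exactly one stratum significant: p1(1 − p2) + p2(1 − p1).

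Worked case, P = 80% and f = 50%: d = 1.96 + 0.84 = 2.80. Then 2.80/√2 = 1.98 and stratum power is about 0.51. Exactly one is significant with probability 2 × 0.51 × 0.49 = 0.50.

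| P | f | p1 | p2 | exactly one |
|---|---|---|---|---|
| 50% | 30% | 0.189 | 0.375 | 0.422 |
| 50% | 40% | 0.236 | 0.330 | 0.410 |
| 50% | 50% | 0.283 | 0.283 | 0.406 |
| 80% | 30% | 0.335 | 0.650 | 0.549 |
| 80% | 40% | 0.425 | 0.583 | 0.512 |
| 80% | 50% | 0.508 | 0.508 | 0.500 |
| 90% | 30% | 0.427 | 0.774 | 0.540 |
| 90% | 40% | 0.536 | 0.709 | 0.485 |
| 90% | 50% | 0.630 | 0.630 | 0.466 |

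The range is about 41% to 55% per comparison. With no effect at all it is 2 × 0.05 × 0.95 = 9.5%.

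**The case against.** A reader might infer that the intake models have no interaction test at all. The SAP does not support that. Its sentence commits to a product term involving the intake covariates, so the test is promised in words and what is missing is its specification.

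A reader might also infer that hypothesis 2 goes untested. It does not. Hypothesis 1 concerns the addition of phytoestrogen-rich foods, which is the randomised arm, and exposure is first defined by arm. Arm by genotype is therefore the direct randomised test of hypothesis 2, and it is written out. One can even read the arm indicator as the covariate that represents intake. That reading is strained, because the SAP lists arm and intake as separate variables and separate models. If it is accepted, the 28 intake models are stratified with no interaction test. If it is rejected, their tests are promised but undefined. The text needs reconciling either way.

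Three further objections have force:

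- No section says that modification will be read from significance in one stratum and not the other. The calculation shows why a product term is needed and does not predict what the trial will do.
- The figures rest on assumed power and strata, and the intake exposures overlap: total phytoestrogens is the sum of isoflavones, lignans and coumestrol. Multiplying 9.5% or 50% by 28 would be wrong.
- Writing `intervention` for `Group_intervention` is evident shorthand, and the variable list in the appendix is not shown. This is only a tidy-up.

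The antibiotic and finasteride strata carry no modification hypothesis, so leaving out a product term contradicts nothing. It is still worth saying whether those strata are descriptive.

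**Conclusion.** The point holds as a mismatch to be reconciled. The SAP describes intake-by-genotype product terms, writes only arm by genotype, and stratifies 28 intake models by genotype with no term specified for them. These models are observational, and the randomised test of hypothesis 2 is unaffected apart from the genotype coding error, which affects every product term.

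The counts (35, 28, 7) come directly from the model lists. The 41-55% and 9.5% figures are per comparison, rest on the assumptions stated with them, and are illustrative only. The point does not undermine the main comparison, but the change is specific and cheap and should be made before analysis.

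**What to change.** 1. Correct `cat_genotype` first, so that each of TT, TC and CC falls in exactly one level.
2. Write `int1 = Group_intervention*cat_genotype` and name it, on Ki-67, as the test of hypothesis 2.
3. State which intake exposures stay stratified by genotype. For each, define its own product with `cat_genotype`, enter it with both main effects and label it exploratory.
4. State whether intake enters continuously, dichotomised or in tertiles. Use a joint 2-degree-of-freedom test for tertiles.
5. State that effect modification is claimed only from the product term and not from comparing significance between strata.
6. For the antibiotic and finasteride strata, either add an exposure-by-stratum term or report them as descriptive only.

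The cost is a few lines of SAP text and a few model terms, with no new data. If all four intake exposures are kept for all seven outcomes, this adds 28 exploratory interaction tests to the 7 arm tests. They will have low power, which is why they need the exploratory label. Keeping fewer exposures in the stratification reduces that number.
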